## 6.4 Assessments after Hospitalization

For participants discharged to home or post-acute care facilities (e.g., LTAC facilities, SNF, or acute rehabilitation facilities) prior to day 90, we will obtain study endpoints by a telephone call with the patient, LAR, or facility staff to assess:

1. Vital status at day 90 and date of death (if applicable)
2. Location at day 90 (home, LTAC/SNF/acute rehab, hospital)
3. Date of discharge home (prior level of care) for participants discharged from the hospital to post-acute care facility
4. Safety endpoints (kidney stones and fall-related fractures)
5. Health-related quality of life by EuroQol (EQ-5D-5L)

The EQ-5D-5L is a brief, validated, reliable, and widely used QOL instrument that determines whether respondents have problems in each of five domains: mobility, self-care, usual activities, pain/discomfort, and anxiety/depression. Responses can be used to calculate a health utility score associated with the given health state that ranges from -0.11 to 1.00 (higher scores are better; 1.00 is perfect health).

At the 90-day follow-up, patients may still be impaired. While proxies differ from primary respondents on almost all instruments, including the EQ-5D-5L, we are hopeful that proxy respondents will not be differentially distributed among intervention and control, allowing us to minimize confounding related to proxy vs. individual responses.

We will collect contact information for the patient and alternative contact information for up to 3 individuals. For participants who we are unable to contact by phone, we will use evidence from the medical record (e.g., healthcare visits after day 90) to identify participants that are still alive. We will also verify duration of survival for participants lost to follow-up or noted to have died using the Centers for Disease Control and Prevention's National Death Index (NDI) and other federal databases. We will use each patient's social security number (SSN) for an exact NDI match. Although we do not plan to collect long-term outcomes as part of primary trial endpoints, we will record Medicare number to facilitate future ancillary studies that wish to link with Medicare data on utilization and functional status.

[figure not shown]

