2.10.2 Secondary Endpoints

Clinical Endpoints

1. **Study hospital length of stay among survivors to day 90:** Study hospital length of stay is defined as the number of days from enrollment (typically the day of hospital admission) to the day of study hospital discharge up to day 90. This endpoint will be analyzed only in survivors because hospital length of stay in those who die in the hospital is non-informative for this endpoint. In addition, we will use survivor average causal effect (SACE) methods to estimate hospital length of stay among participants that would have survived in both treatment and control groups.⁵⁰ Accordingly, these methods adjust for the impact of differential survival between treatment groups.
2. **Healthcare facility length of stay among survivors to day 90:** Healthcare facility length of stay is the time spent in another hospital or healthcare facility (e.g. long-term acute care [LTAC] hospitals or acute rehabilitation/skilled nursing facility), for the subgroup of participants that were discharged to another healthcare facility after the initial hospitalization. This measure is defined as the number of days from initial hospital discharge to the first facility discharge to home (pre-hospitalization level of care) up to day 90. Healthcare facility LOS is zero for patients discharged to home (pre-hospitalization level of care) from the study hospital. This endpoint will be analyzed only in survivors using SACE methods because healthcare facility length of stay in those who die during the follow-up period is non-informative for this endpoint.
3. **Alive and home at day 90:** This endpoint is the proportion of participants who have survived and are present at home, defined as pre-hospitalization level of care, at day 90.

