3.1 Statistical Methods for Main Manuscript

All analyses are intention to treat, that is, all randomized participants within each cohort (screened deficient, confirmed deficient) will be included in the analyses specified for each cohort. The confirmed deficient cohort is the primary efficacy cohort per the protocol.

All significance testing will be two-tailed at $\alpha = 0.05$ with no adjustment made for multiple comparisons³

With the exception of the primary outcome, analysis is based on all available data with no imputation of missing data.

The causal clinical effect of treatment on outcomes defined only in patients who are on study is complicated by potential case mix imbalance between the treatment groups due to differential recovery and mortality. However, the proposed statistical methods for these outcomes maintain the correct comparison-wise Type I error rate under the global null of no treatment effect whatsoever on any patient.

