3.2 Primary Endpoint

The primary outcome of all-cause, all-location mortality to day 90 will be compared between treatment groups on the risk difference scale using a generalized linear model with a binomial distribution function and identity link function. This is equivalent to a Z-test comparing the difference between two proportions but extends naturally to assessment of sub-group by treatment interactions on the risk difference scale.

For participants that have missing 90-day mortality, we will use the Centers for Disease Control and Prevention's National Death Index (NDI) to determine vital status, using each patient's social security number (SSN) for an exact NDI match or other identifying information if SSN unavailable. If none of the patients with missing 90-day mortality are found in the NDI to have died within 90 days we will assume they are all alive at 90 days. If any are known to be deceased, we will impute 90-day mortality for the remaining patients with unknown status using a multi-state model to estimate the transition probabilities across recorded states (in hospital, post hospital facility, home, death). In addition, we will include a sensitivity analysis based on the assumption that the probability of death increases with elapsed time since last follow up.

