3.3 Secondary Endpoints

3.3.1 Clinical Endpoints

Hospital mortality to day 90, and alive and home (prior level of care) at day 90, and 28 day mortality will be compared between treatment groups using Pearson's chi-square test.

Hospital length of stay and healthcare facility length of stay will be analyzed only in survivors to day 90. We will use survivor average causal effect (SACE) methods to estimate each outcome among participants that would have survived in both treatment and control groups⁴. The SACE methodology includes a model for predicting survival using baseline covariates. The covariates used will be sex, age, Charlson, SOFA, baseline 25OHD as measured by LCMS, and race/ethnicity (non-Hispanic white versus other).

Ventilator-free days to day 28 will be compared between treatment groups using a t-test.

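### Alive and home at day 90 is analysed on available data only, so among participants who cannot be reached the deaths count as failures and the survivors drop out

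*SAP*

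**What the plan says.** SAP 3.1 sets one missing-data rule for all non-primary outcomes: "With the exception of the primary outcome, analysis is based on all available data with no imputation of missing data". The same section says that the analyses include every randomized participant in the relevant cohort.

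SAP 2.10.2 defines the endpoint: "This endpoint is the proportion of participants who have survived and are present at home", with home meaning the level of care before hospitalization. SAP 3.3.1 names only the test: hospital mortality and "alive and home (prior level of care) at day 90, and 28 day mortality will be compared between treatment groups using Pearson's chi-square test". It gives no missing-data rule and no sensitivity analysis for this endpoint.

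Under Protocol 6.4, day-90 location for participants discharged earlier comes from a telephone call to the patient, the representative or facility staff. When nobody can be reached, the back-up sources are aimed at survival. Protocol 6.4 says "we will use evidence from the medical record (e.g., healthcare visits after day 90) to identify participants that are still alive". SAP 2.10.1 adds obituaries and calls to healthcare facilities. SAP 3.2 uses the "National Death Index (NDI) to determine vital status" for those still missing.

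If the index shows no death within 90 days among the missing, SAP 3.2 assumes that all of them are alive. Otherwise it will "impute 90-day mortality for the remaining patients with unknown status using a multi-state model", whose states are hospital, post-hospital facility, home and death. That model is specified for mortality only. SAP 2.10.1 expects fewer than 5% to have unknown vital status after all sources.

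**The concern.** A death settles this endpoint without any location, whereas a survivor needs a location. The back-up sources are directed at finding out who died and who lived, not where survivors were living on day 90. Among participants who cannot be reached, only those who survived can therefore lack the outcome. Available-case analysis keeps the recovered deaths in the denominator and removes survivors of unknown location.

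The anticipated figure of under 5% does not limit the problem. It counts unknown vital status. A clinic visit after day 90, or no match in the death index, can settle survival and leave residence unknown, so location may be missing more often.

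Two inconsistencies follow. The same participant can count as alive in the primary analysis and be absent from alive and home, so two rows of one results table rest on different denominators. The statement that all randomized participants are included also cannot be met for this endpoint. At stake are the reported proportion in each arm and, if loss of location differs between arms, the treatment comparison.

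**Working it through.** **The plan's own figure.** The documents give no number for alive and home. Their stated power of 87.4% for mortality (SAP 2.9) serves as a check on the design inputs. With 1200 per arm, 20% versus 15% and one-sided 0.025, a fixed design gives 89.7%. The three-interim design with the 0.025t⁴ spending function gives 89.3% without futility stopping. It gives 87.5% under an assumed futility rule of predictive probability below 5%. The inputs are consistent with the stated power.

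**Inputs.**
- From the documents: mortality d = 20% (control) and 15% (vitamin D), and 2400 confirmed deficient participants, that is 1200 per arm.
- Assumed: share of survivors at home h = 0.75 (range 0.60–0.90); share of survivors without a location, Lh if at home and Lf if elsewhere; every unreached death is recovered.

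**Formula.** True proportion = (1−d)h. Available-case proportion = (1−d)h(1−Lh) / [(1−d)h(1−Lh) + (1−d)(1−h)(1−Lf) + d].

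**1. Equal loss at home and elsewhere (Lh = Lf = L), h = 0.75.**
- Control, true 60.0%. L = 5%: 0.570/0.960 = 59.4%, bias −0.6 points. L = 10%: 0.540/0.920 = 58.7%, bias −1.3.
- Vitamin D, true 63.75%. L = 5%: 0.6056/0.9575 = 63.25%, bias −0.5. L = 10%: 0.5738/0.915 = 62.7%, bias −1.05.
- Over h = 0.60–0.90, control bias is −0.5 to −0.75 at 5% loss and −1.0 to −1.6 at 10%.
- If unreached deaths were not recovered either, the bias would be zero. One-sided recovery is the cause.

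**2. Direction.** The available-case proportion exceeds the truth when Lf/Lh > [1−(1−d)h] / [(1−d)(1−h)]. At d = 20% and h = 0.75 this is 0.40/0.20 = 2. At d = 15% it is 0.3625/0.2125 = 1.7. Understatement is therefore not guaranteed. If only home survivors are lost, control bias is larger: −1.2 points at 5% and −2.6 at 10%.

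**3. Between-arm difference, mortality 20% versus 15%, true difference 3.75 points, h = 0.75.**

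| Loss, control | Loss, vitamin D | Difference read |
|---|---|---|
| 5% | 5% | 63.25 − 59.38 = 3.88 |
| 10% | 10% | 62.70 − 58.70 = 4.01 (before rounding) |
| 12% | 6% | 0.59925/0.949 − 0.528/0.904 = 63.15 − 58.41 = 4.74 |
| 6% | 12% | 0.561/0.898 − 0.564/0.952 = 62.47 − 59.24 = 3.23 |

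**4. No treatment effect, mortality 20% in both arms.** With equal loss the difference is 0 and two-sided type I error is 5.0%. Loss of 12% versus 6% gives 59.24 − 58.41 = 0.8 points. Loss of 5% versus 10% gives 0.7 points at h = 0.75, with a standard error of about 2.1 points and type I error of 6.2%. Over h = 0.60–0.90 this becomes 0.5–0.8 points and 5.8–7.1%.

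**The case against.** The SAP nowhere says that deaths from the index enter this endpoint as failures or that survivors of unknown location are dropped. That is true. Both are inferences, but they follow from the endpoint definition and the no-imputation rule, and the plan offers no other rule.

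A reader might infer that the endpoint is certainly understated in both arms. The documents do not support that. Some lost survivors are themselves not at home, and no loss rate by location is given. Step 2 shows that the sign can reverse.

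A reader might also infer that the plan manufactures a treatment benefit. It does not. With equal loss and no effect the test is valid, and unequal loss can shrink the difference as easily as inflate it. The trial is double-blind with one dose and a matched placebo, and nothing in the documents points to unequal follow-up.

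The loss may be modest. Up to three alternative contacts are collected, and calls to facilities could establish location as well as survival. Recovery of deaths may be incomplete, since the social security number is only requested at consent, and that would reduce the bias. These points limit the size of the problem and leave the mechanism intact.

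Finally, the multi-state model cannot simply be reused. SAP 3.2 fits it only if some of the missing are found to have died. That objection stands and shapes the fix.

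**Conclusion.** The point holds as a minor flaw in the analysis of one secondary endpoint. Followed as written, the plan gives missingness that depends on survival, which is part of the outcome.

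If location is lost about equally often at home and elsewhere, each arm's proportion is understated. In control this is about 0.6 points at 5% loss and 1.3 points at 10%. With a real mortality difference of 15% versus 20%, equal loss of 5–10% inflates a true 3.75-point difference by only 0.1–0.3 points, well below its standard error of about 2 points. Larger distortion needs loss that differs between arms, and its sign depends on which arm loses more.

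These figures rest on assumed home shares and loss rates and on full recovery of deaths. Only the mortality rates and cohort size come from the documents.

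**What to change.** In SAP 3.1, exempt alive and home at day 90 from the no-imputation rule, and in SAP 3.3.1 state how it is handled:

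- Score known deaths by day 90 as failures.
- For participants who are known alive, assumed alive or imputed alive but have no day-90 location, multiply impute home status from the multi-state model in SAP 3.2. Within each imputation, a participant imputed dead is a failure.
- Fit the model for this endpoint whether or not the death index finds any death among the missing.
- Report the complete-case result and best-case and worst-case bounds as sensitivity analyses, with the number of survivors lacking a location in each arm.

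The bounds are too wide to stand alone. At 5% loss in control, 0.80 × 0.05 = 4% of the arm is unknown, so the proportion runs from 57% to 61%.

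The cost is a few sentences in the SAP and a little extra analysis. No new data are needed, since the model already has a home state. The downside is reliance on the model for the few participants with unknown location, which the sensitivity analyses make visible.

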3.2 Primary Endpoint

The primary outcome of all-cause, all-location mortality to day 90 will be compared between treatment groups on the risk difference scale using a generalized linear model with a binomial distribution function and identity link function. This is equivalent to a Z-test comparing the difference between two proportions but extends naturally to assessment of sub-group by treatment interactions on the risk difference scale.

For participants that have missing 90-day mortality, we will use the Centers for Disease Control and Prevention's National Death Index (NDI) to determine vital status, using each patient's social security number (SSN) for an exact NDI match or other identifying information if SSN unavailable. If none of the patients with missing 90-day mortality are found in the NDI to have died within 90 days we will assume they are all alive at 90 days. If any are known to be deceased, we will impute 90-day mortality for the remaining patients with unknown status using a multi-state model to estimate the transition probabilities across recorded states (in hospital, post hospital facility, home, death). In addition, we will include a sensitivity analysis based on the assumption that the probability of death increases with elapsed time since last follow up.

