### 6.3.1 Specimen Collection

We will collect 15 mL of blood at baseline (within 2 hours of randomization) for all randomized participants and 15 mL of blood at study day 3 for approximately the first 300 randomized participants (300 participants with match pairs of baseline and day 3 samples). We will measure plasma 25OHD on baseline samples for all randomized participants and on study day 3 samples for approximately the first 300 randomized participants. Additionally, we will measure plasma IL-6 at baseline and on study day 3 for approximately the first 300 randomized participants. Some of the blood collected on randomized participants at baseline will also be used for banking of plasma and DNA for future research.

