**Table 1 Specimen Collection Schedule**

Subjects	Collection Type	Draw Time Points
All randomized subjects	Plasma for 25OHD	Baseline
	Plasma for banking	
	Whole blood for DNA banking	
Approximately the first 300 randomized subjects	Plasma for IL-6	Baseline & Day 3
	Plasma for banking	Day 3
	Plasma for 25OHD	Day 3

The 25OHD and IL-6 samples will be shipped to a central lab for batched measurements. The baseline 25OHD samples will be measured by the LC/MS/MS method and compared to the screening test results, initially in monthly increments for quality control purposes. The samples for future research (plasma and whole blood for DNA) will be shipped to the network central repository. All samples will be identified by a coded number during shipment and storage in both the central repository and central lab.

The primary purpose of this trial is to evaluate efficacy and safety of the proposed vitamin D intervention, and we have attempted to limit additional data and specimen collection that extend beyond this aim. Accordingly, we designed the limited biospecimen collection plan to confirm that the vitamin D dose successfully corrects vitamin D deficiency and changes an important biomarker in critical illness (IL-6); this requires a small subsample (n=300) to evaluate. In addition, we will be able to stratify results based on clinical variables and vitamin D levels to see if there are subgroups that may have more or less potential to benefit. Although additional explanatory and mechanistic data collection would be beyond the scope (and budget) of the present trial, we will store baseline plasma/DNA to facilitate additional (ancillary) studies that would be potentially useful in explaining negative or positive results.

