 - i. Review the first CXR (or CT) performed on each ventilated day with valid P/F or imputed P/F <300 (to day 7). If no chest imaging studies are present that day, site investigators may review imaging one day before or after to determine if ARDS imaging criteria met.
 - ii. Assess if the images are consistent with ARDS (bilateral opacities not fully explained by effusions, lobar/lung collapse, or nodules). If equivocal, the reviewing investigator will adjudicate with additional investigators.
7. **Change in organ failure severity to day 7:** We will measure acute organ failure severity daily to day 7 for three key organ systems: acute hypoxemic respiratory failure, acute kidney injury, and cardiovascular failure (i.e., shock). We will measure acute hypoxemic respiratory failure using data from the ARDS assessment, except this outcome does not require chest imaging consistent with ARDS. We will measure acute kidney injury by highest daily creatinine values or new use of dialysis/ renal replacement therapy (chronic dialysis

participants are excluded). We will measure cardiovascular failure by highest daily dose of vasopressors (epinephrine, norepinephrine, dopamine, phenylephrine, or vasopressin).

8. **Plasma 25OHD levels:** In addition to the screening vitamin D test (for trial entry), we will measure gold-standard plasma 25OHD levels at baseline for all randomized participants and at day 3 in the first 300 randomized participants to confirm biomarker response to the intervention. The gold-standard test will be done in batch using LC/MS/MS methods. Individual results will not be available to investigators and coordinators to avoid unblinding. Based on pre-specified rules and in consultation with the DSMB (who will have access to additional adverse event data), we may require changes to the vitamin D dose or extend the duration of 25OHD/calcium monitoring.
9. **Plasma IL-6 levels:** We will measure plasma IL-6 levels at baseline and day 3 in the first 300 randomized participants in batch concurrent with 25OHD testing. IL-6 is a pro-inflammatory cytokine associated with increased incidence and severity of ARDS severity and worse clinical outcomes. Vitamin D may improve outcomes in critically ill patients by reducing levels of IL-6 (either causal association or as a result of improved recovery)

Safety Endpoints

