3.3.2 Physiological Endpoints

Binary endpoints will be compared between treatment groups using Pearson's chi-square test.

Ordinal endpoints will be scored as 1,2,3, ... and compared between treatment groups using the CMH mean score test.

Continuous endpoints will be compared between treatment groups using a t-test with two exceptions. The highest creatinine and CV SOFA score will be analyzed controlling for baseline value using repeated measures ANOVA with a treatment by time interaction and shared intercept at time 0 (baseline). This model is equivalent to ANCOVA controlling for baseline but is able to make use of all available data.

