- Baseline 25OHD level (by the LCMS): <12, 12-19, 20-29, ≥30 AND <10, 10-19, 20-29, ≥30 AND <20, ≥20
- Baseline renal function: eGFR 15 (or on dialysis), 15-29, 30-59, 60-89, ≥90
- ARDS risk factor: sepsis, pneumonia, shock, mechanical ventilation, other AND infectious, non-infectious
- LIPS score: <4, ≥4
- Pre-randomization mechanical ventilation status: Y, N
- Pre-randomization presence of ARDS: Y, N
- Source of ICU admission: ED, other
- ICU destination: MICU, other
- Modified intention to treat (received full study drug dose without vomiting within 1 hour): yes, no

Figure. Time to Mortality to Day 90 for screened deficient (all randomized)

- Baseline LCMS <12
- Baseline LCMS 12 to <20
- Baseline LCMS ≥20

Table. Primary and Main Secondary Endpoints for screened deficient (all randomized)

Table. Adverse Events and Safety Outcomes for confirmed deficient, confirmed not deficient (LCMS \geq 20), and screened deficient (all randomized)

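### IL-6 gets a t-test with no stated scale and no baseline term, although paired samples exist and the SAP already has a suitable model; mortality could gain one supportive adjusted estimate

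*SAP*

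**What the plan says.** **IL-6.** SAP 2.10.2: "We will measure plasma IL-6 levels at baseline and day 3 in the first 300 randomized participants". Protocol 6.3.1 aims for "300 participants with match pairs of baseline and day 3 samples" and, in the text under Table 1, says of showing that the dose corrects deficiency and changes IL-6 that "this requires a small subsample (n=300) to evaluate". No power figure is given. The results table in SAP 3 lists the endpoint only as IL-6 to day 3, for the confirmed deficient cohort. The supplementary outline in SAP 4 repeats the main endpoint table for all randomized participants. The test is fixed in SAP 3.3.2: "Continuous endpoints will be compared between treatment groups using a t-test with two exceptions". The exceptions follow: "The highest creatinine and CV SOFA score will be analyzed controlling for baseline value using repeated measures ANOVA", with a shared intercept at time 0, which the SAP calls equivalent to ANCOVA.

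**Mortality.** SAP 3.2 compares 90-day mortality as a risk difference from a binomial identity-link model without covariates, and states: "This is equivalent to a Z-test comparing the difference between two proportions". Predictors of survival are named in SAP 3.3.1: "The covariates used will be sex, age, Charlson, SOFA, baseline 25OHD as measured by LCMS, and race/ethnicity". They are listed there for the survivor average causal effect (SACE) models, which SAP 3.3.3 uses again for EQ-5D-5L. No covariate-adjusted overall mortality effect is planned, even as support.

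**The concern.** A paired baseline sample is collected for IL-6, and the suitable model sits in the same section for two other endpoints, but IL-6 is not given it. The scale is also open. For a right-skewed marker the choice between raw and log values can decide whether about 240 confirmed participants (80% of 300) are enough, and the protocol's statement that 300 suffice cannot be checked without it. IL-6 is the only inflammatory marker among the listed endpoints, so an imprecise null there would be hard to interpret.

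For mortality the stake is smaller. A supportive adjusted estimate fixed in advance gives some precision and a ready answer if age or severity differ between arms by chance.

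**Working it through.** **1. The plan's own power figure, to show that the primary test is sound.** Inputs from SAP 2.9 and Protocol 7.1: 20% v 15%, 3000 randomized, 80% confirmed (1200 per arm), one-sided 0.025, looks at 750, 1500 and 2250, spending 0.025t^4.
- Fixed design: SE = sqrt[(0.20×0.80 + 0.15×0.85)/1200] = 0.01548. Power = Φ(0.05/0.01548 − 1.96) = Φ(1.27) = 89.8% (89.7% by a standard two-proportion power routine).
- Efficacy looks only: 89.4-89.5%.
- With a predictive-probability futility stop: 87.8% at a 5% cut-off and 86.0% at 10%. The cut-off is assumed, because the documents give none.
- The stated 87.4% lies between these. Simulated cumulative success of 0.016, 0.245 and 0.64 agrees with the protocol table's 0.016, 0.244 and 0.637.

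The stated power therefore does not depend on adjustment.

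**2. IL-6.** From the documents: 300 people with paired samples, 80% confirmed, so 240 (120 per arm), two-sided 0.05. Assumed, because the documents give no values: lognormal data, log SD s = 1.0-1.5, correlation ρ = 0.4-0.6 between baseline and day 3, true ratio 0.67, so a log difference of 0.400.

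Log-scale SE is s·sqrt(2/120) = 0.1291s for the day-3 t-test. It is multiplied by sqrt(1−ρ²) for the baseline-adjusted model. Power is Φ(0.400/SE − 1.96):

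| s | ρ | log day-3 t-test | log, baseline-adjusted | gain (points) |
|---|---|---|---|---|
| 1.0 | 0.4 | 87.3% | 92.3% | 5.0 |
| 1.0 | 0.6 | 87.3% | 97.2% | 9.9 |
| 1.5 | 0.4 | 54.3% | 61.7% | 7.4 |
| 1.5 | 0.6 | 54.3% | 73.4% | 19.1 |

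Simulation agrees: log day-3 54-87%, log baseline-adjusted 62-97%. A raw day-3 t-test reaches only 25-69%.
- Raw to log adds 69 to 87 = 18 points at s = 1.0 and 25 to 54 = 29 points at s = 1.5.
- The baseline term then adds about 8-10 points between matching ends of the ranges (54 to 62, 87 to 97), and 5-19 over the four settings in the table.
- With 300 people: raw 29-78%, log day-3 64-94%, log adjusted 71-99%.
- With ratio 0.75 and 240 people: raw 15-42%, log day-3 31-61%, log adjusted 36-80%.
- With no true effect the adjusted model rejects in 4.8-5.3% of simulations. The raw t-test is not inflated either. It is only weak.

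**3. Mortality.** Simulated trials with the plan's looks and boundaries (no futility stop) compared the crude Z-test with a standardized logistic model. At assumed c-statistics of 0.62, 0.67 and 0.70 the variance falls by 2.6%, 5.4% and 7.7%.
- Equivalent participants: 2400/0.974 − 2400 = 64; 2400/0.946 − 2400 = 137; 2400/0.923 − 2400 = 200.
- Sequential power rises by 0.7, 1.5 and 2.2 points.
- Closed-form check from 89.8%: Φ(3.230/sqrt(1−fall) − 1.96) = 90.5%, 91.3% and 92.0%, the same gains.
- With 30% of SOFA missing at c = 0.67, the gain is 1.2 points.

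**The case against.** The strongest reply is that nothing here is an error. The mortality Z-test is valid and matches the binomial comparison behind the sample size, and the SAP gives a reason for the identity-link model: it carries over to subgroup interactions on the risk-difference scale. That stands, and it is why the test should remain the governing one.

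The reply on IL-6 is that most of the loss is a matter of scale under an assumed distribution, not of an unused baseline. That is largely right, and the two parts are shown separately above. A raw-scale analysis would still be permitted as the SAP is written.

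A reader might infer more than the documents support:
- **That baseline data are ignored in general.** They are not. They enter the creatinine, CV SOFA, EQ-5D-5L and SACE analyses, the 25OHD spline and the subgroups.
- **That four t-tests (raw or log, day 3 or change) are all permitted.** If an analyst tried all four and reported the best, 13-14% of null trials would give p<0.05. But the SAP says change or adjusted where it means it, so the ordinary reading is the day-3 level, and only the scale is open. Picking the better of raw and log then gives 7.0-7.6%.
- **That the adjusted mortality estimate should become primary.** The futility rule in Protocol 7.1 predicts success from the death rates by arm, and SAP 3.2 may impute unknown vital status by a multi-state model. Both would have to be reworked for a gain of about two points at most.
- **That leaving the hospital stratum out of the model is a fault.** In simulation it made the SE at most about 3% too large, which is conservative.

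**Conclusion.** The point holds as a low-cost improvement, mainly for IL-6. The planned t-test is valid, but it ignores a paired baseline and leaves the scale open. Under the stated assumptions, log IL-6 in the SAP's own shared-baseline model has 62-97% power where a raw day-3 t-test has 25-69%. The size rests on lognormality, the log SD and the correlation, none of which the documents give. The direction is safer: the log scale suits a skewed marker, and a correlated baseline does not cost precision in about 240 people. Baseline adjustment does not solve day-3 samples missing because of death or discharge.

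IL-6 is secondary, so the primary conclusion is unaffected. For mortality, only a supportive adjusted analysis is warranted, worth about 0.7-2.2 points at assumed c-statistics.

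**What to change.** 1. **SAP 3.3.2 and the endpoint tables.** Add log IL-6 at day 3 as a third exception, analysed in the shared-baseline model already used for creatinine and CV SOFA. Report a geometric mean ratio with 95% CI in both the confirmed deficient and all-randomized cohorts. State a rule for values below the assay limit.
2. **SAP 3.2.** Keep the two-proportion Z-test and say that it governs the primary conclusion. Before unblinding, prespecify one supportive covariate-adjusted risk difference: a logistic model with treatment, age, sex, SOFA and Charlson, standardized over the cohort, shown beside the crude estimate. Protocol 6.2 collects SOFA as clinically available, so add a missing-SOFA rule, for example the mean over both arms plus a missing indicator. Say how imputed vital status enters.

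Cost: SAP wording and some programming, with no new data and no change to boundaries or alpha. IL-6 would be read as a ratio. The two mortality results can disagree: at 20% v 15%, only the adjusted test succeeds in 1.6-3.3% of simulated trials and only the crude test in 0.9-1.1%. That is why the governing test must be named in advance.
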